**The anti-inflammatory effect of prophylactic macrolides on children with chronic lung disease: a double blinded RCT**

**NCT02544984**

**Version date: 10/09/2015**

## **Research Aims**

### **Primary Aims:**

1. To determine if prophylactic use of azithromycin will reduce the total number of unscheduled face-to-face physician visit for respiratory related illness in a clinic, urgent care, emergency room or hospital setting during the 3-6 month study period, and subsequent 2 months follow-up.

### **Secondary Aim:**

1. To determine if the administration of azithromycin will have similar number of adverse side effects, or adverse events leading to unscheduled clinic, urgent care, emergency room or hospital visit as compared to placebo during the 3-6 month study period and the following 2 months.
2. To determine if the use of azithromycin will reduce healthcare cost associated with respiratory illness during the 3-6 month study period and 2 month follow-up period.

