## **Study Design and Methods**

### *Overview:*

This pilot randomized control trial (RCT) will enroll 92 children from 6 months to <6 years of age that have chronic lung disease (CLD) such as bronchopulmonary dysplasia during two seasons of respiratory illnesses defined as 1st October to 31st March of each year (2015-2016 Season and 2016-2017 Season). If the minimum number of patients (n=92) in Season 1 is achieved, we will then perform an interim analysis of the data. These children will all be patients who receive their primary medical care from either the High Risk Children Clinic or the similar High Risk Infant Clinic that cares for premature infants from discharge until age 2. Clinic records will be screened to determine eligibility. Patients that have parental consent will be given a baseline EKG, a nasal aspirate, an oscillometer reading (over 2 years of age only), and a three to six month supply of either the medication or the placebo at an initial study visit. Both medications will be taken once a day for three days a week: Monday, Wednesday and Friday. The azithromycin medication will be dosed at 5 mg/kg/day. Adjustments in dosage amount will be made with any new weights obtained during the trial period. Any child that is eligible to receive Palivizumab will be given this every 28-30 days in clinic as per usual care. Patients will be followed on a monthly basis and closely monitored for adverse reactions; this will occur by phone, in clinic during their regularly scheduled appointments, and/or during any necessary illness visits. Any children with adverse reactions will discontinue the medication, but will continue to be followed clinically. At any clinic visit in which a child presents with respiratory infections, including pneumonia,

upper respiratory illness, bronchiolitis, etc., he/she will have an additional nasal aspirate and/or tracheal aspirate if applicable and an oscillometer reading (only for children >2 years) performed. At the completion of the 3-6 months treatment phase, each child will have a final nasal aspirate and/or tracheal aspirate if applicable, and an oscillometer reading performed. Data will continue to be collected for the following 2 months (April 1st to May 31st), to monitor for respiratory illnesses and possible side effects.

*Study Population:*

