#### *Study Procedures:*

Patients will be randomized by the REDCap statistical program in a double blind manner. Parents will then be provided with a medication or placebo for the duration of the study. Patients would be recruited for this study on a rolling basis from October 1st to December 31st, and all patients completing the intervention part of the protocol on 31st March at the end of the season. Half of the patients will receive azithromycin at a

dose of 5 mg/kg to be given once a day on Monday, Wednesday, and Friday. The other half, the control group, will be provided with a placebo medication of similar taste, color, texture, and consistency, also to be taken once a day on Monday, Wednesday, and Friday. Both the study medication and the placebo will be dispensed from Corner Compounding Pharmacy, mixed with a fish-oil base to ensure a shelf life of more than six months, and flavored with citrus to improve palatability. Parents will be contacted biweekly, either in clinic or by phone, to monitor for any adverse reactions, including rash, nausea, vomiting, diarrhea, or abdominal cramping. If a significant adverse reaction occurs, the medication will be discontinued. If an allergic reaction (such as rash or shortness of breath) is noted, the blind will be broken by Research Coordinator [name], who is not involved with the project. This un-blinding will be done to note if it is an allergy to the medication.

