## **Study Outcomes**

1. In the treatment group, we expect a 20% total reduction in face to face encounters (defined as unscheduled sick visits, emergency room visits, and hospital admissions) for respiratory symptoms with the prophylactic use of azithromycin, as compared to the control group.
  - a. In the treatment group, we expect to have a 20% decrease in the number of unscheduled sick visits due to respiratory illness during the 3-6 month study period with the prophylactic use of azithromycin, as compared to the control group .
  - b. In the treatment group, we expect to have a 20% decrease in the number of Emergency Room visits due to respiratory illness during the 3-6 month study period with the prophylactic use of azithromycin, as compared to the control group.

- c. In the treatment group, we expect to have a 20% reduction in the number of hospital admissions due to respiratory illness during the 3-6 month study period with the prophylactic use of azithromycin, as compared to the control group.
2. In the treatment group, we expect a 10% total reduction (as compared to baseline) in the level of myeloperoxidase in the nasopharyngeal secretions collected during respiratory illnesses that require a face to face provider encounter, as compared to the control group.
3. In the treatment group, we expect a 10% total reduction in the level of pro-inflammatory cytokines in the nasopharyngeal secretions collected during respiratory illnesses that require a face to face provider encounter, as compared to the control group.
4. In the treatment group, we expect a 10% reduction from baseline in the level of airway obstruction as measured by a tremoFlo Airwave Oscillometry System during the 3-6 month study period, respiratory illness and at the conclusion of the intervention phase.
5. We expect no significant difference in adverse side effects between the treatment group receiving the macrolide and the control group receiving the placebo during the 4 month study.
6. We expect the intervention to be cost-effective from a healthcare system perspective.

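### Safety is compared on a count that includes two off-drug months: a true on-drug doubling would show as 1.60 to 1.75, and lower once early stopping is counted

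*Combined protocol and SAP*

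**What the plan says.** The Secondary Aim section, item 1, compares the arms on a "similar number of adverse side effects, or adverse events leading to unscheduled clinic, urgent care, emergency room or hospital visit as compared to placebo". The counting window covers treatment and a further two months off it. Time on product varies because of the calendar. Under Study Procedures, enrolment is staggered and closes at the end of December, while the intervention ends for everyone on 31 March. Under Overview, "Data will continue to be collected for the following 2 months", that is, through the end of May. So 2 of each child's 5 to 8 months are off drug by design.

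Overview also says: "Any children with adverse reactions will discontinue the medication, but will continue to be followed clinically". Study Procedures puts the trigger differently: "If a significant adverse reaction occurs, the medication will be discontinued".

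Study Outcomes, item 5, gives the criterion: "We expect no significant difference in adverse side effects between the treatment group receiving the macrolide and the control group". The period named there is a 4-month study, which is neither 3 to 6 months nor treatment plus 2 months.

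The Data Analysis Plan names an intent-to-treat approach. No on-treatment window, person-time denominator, margin, expected adverse-event rate or power is given for safety.

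**The concern.** Drug-caused reactions arise mainly while the child takes the drug. Time off product contributes events at the background rate in both arms, so adding it to the count moves the ratio toward 1. Such dilution is usually conservative, because it makes a benefit harder to show. Here the hoped-for finding is similarity, judged by the absence of a significant difference and with no margin, so dilution favours that conclusion. At stake is whether on-drug harm would be seen in medically complex children, aged 6 months to under 6 years, who take an antibiotic for 3 to 6 months.

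**Working it through.** **The plan's own figure.** There is none for safety. The only sizing statement concerns the encounter rate: 2 × (1.96 + 0.8416)² × 1.66² / 1² = 43.3, or 44 per arm. That agrees with the stated 45 per group but says nothing about adverse effects.

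**Inputs from the documents.** Treatment lasts T = 3 to 6 months. The window is T + 2 months. Children who stop remain in follow-up.

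**Assumptions.** The background rate is r events per child-month in both arms, 2r while on azithromycin, and r again as soon as it stops. A fraction f of reactions stops product. Neither r nor f is given in the documents.

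**Formula.** Let E be the expected time on azithromycin.
- Azithromycin count = 2rE + r(T + 2 − E) = r(T + 2) + rE
- Placebo count = r(T + 2)
- Ratio = 1 + E/(T + 2)
- With no early stopping E = T; otherwise E = (1 − exp(−2rfT)) / (2rf)

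**Step 1: off-drug months only (E = T).** The ratio is (2T + 2)/(T + 2), and r cancels.
- T = 3: 8/5 = 1.60
- T = 4.5: 11/6.5 = 1.69
- T = 6: 14/8 = 1.75

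**Step 2: add early stopping.** For example, with r = 0.20, f = 1 and T = 6, E = (1 − exp(−2.4))/0.4 = 2.27 and the ratio is 1 + 2.27/8 = 1.28.

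| r per child-month | Every reaction stops (T = 3; T = 6) | Half stop (T = 3; T = 6) | Azithromycin children with a reaction by T (T = 3; T = 6) |
|---|---|---|---|
| 0.01 | 1.58; 1.71 | 1.59; 1.73 | 6%; 11% |
| 0.05 | 1.52; 1.56 | 1.56; 1.65 | 26%; 45% |
| 0.10 | 1.45; 1.44 | 1.52; 1.56 | 45%; 70% |
| 0.20 | 1.35; 1.28 | 1.45; 1.44 | 70%; 91% |

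A ratio of exactly 1.3 needs r of about 0.27 (T = 3) or 0.19 (T = 6), with 80% or 89% of azithromycin children stopping.

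**Step 3: the 4-month window.** If Study Outcomes item 5 means 4 on-drug months only, the calendar dilution disappears. Stopping with continued follow-up still dilutes. The ratio is then 1 + E/4, which with every reaction stopping product is 1.82 at r = 0.05 and 1.50 at r = 0.20.

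**Step 4: does an on-product analysis do better?** Simulated power with 46 per arm (half of 92), T uniform on 3 to 6 months, a true ratio of 2.0 and no between-child heterogeneity; figures are good to about two points.

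| Stopping | r | Full-window count | Log-rank, first on-product reaction | Rate per child-month on product |
|---|---|---|---|---|
| None | 0.05 | 36% | 40% | 43% |
| None | 0.10 | 62% | 62% | 74% |
| None | 0.20 | 88% | 79% | 96% |
| Every reaction | 0.05 | 30% | 41% | 40% |
| Every reaction | 0.10 | 39% | 61% | 62% |
| Every reaction | 0.20 | 42% | 79% | 77% |

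The on-product rate ratio recovers about 2.0 under either rule. The log-rank test gains over the count only when reactions usually stop product; with no stopping the gain vanishes and then reverses.

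**The case against.** The full-window count is a legitimate intent-to-treat quantity, and following children after the last dose is sensible for catching late effects. The aim speaks of a number, not a ratio. With no early stopping the excess is rT events per child whether or not the two months are counted, so on the difference scale they add noise rather than bias. This stands: the measure is not invalid, and the gap is the missing on-drug comparison beside it.

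The stopping part of the dilution does not cover the whole measure either. Adverse events that lead to a visit but are not reactions need not stop product, and for those only the calendar effect applies. If azithromycin effects persist after the last dose, the dilution is smaller.

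A reader might infer that the plan itself turns a doubling into 1.3 to 1.6. The documents do not support that range: it needs an event rate they never give and a stop at every reaction, while the calendar alone gives 1.60 to 1.75. A reader might also infer that a time-to-first-reaction test is generally more powerful. The no-stopping rows of the power table contradict this, and the two stopping statements conflict, so neither set of rows can be taken as the plan.

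**Conclusion.** The concern holds in a limited form. Under the window in the Secondary Aim, and with no effect after the last dose, a true on-drug rate ratio of 2.0 appears as 1.60 to 1.75 from the off-drug months alone, whatever the event rate. Early stopping with continued follow-up lowers it further, to about 1.3 at roughly 0.2 background events per child-month with every reaction stopping product. That end would mean 70% to 91% of azithromycin children reacting, so it is an extreme. The direction favours the similarity conclusion.

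An on-product rate removes this dilution under the model. It had more power than the full-window count at every rate shown (0.05 and above); no gain is claimed below that. With strong between-child heterogeneity and stopping at reactions, even the on-product ratio can fall somewhat short of 2.0, because susceptible children leave on-product time sooner in the azithromycin arm.

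**What to change.** Change the analysis wording for Secondary Aim item 1 and Study Outcomes item 5:
- **Main safety comparison:** the rate of adverse effects per child-month on study product, as a rate ratio with a 95% CI and a variance that allows for between-child heterogeneity.
- **Support:** time to first on-product reaction, and the proportion in each arm stopping for a reaction.
- **Retain:** the full-window intent-to-treat count, with the 2 off-drug months also reported separately for late effects.

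Reconcile three sets of statements: the safety window (treatment plus 2 months against a 4-month study); which reactions stop product (Overview against Study Procedures); and whether the 2 months run over April and May or from the last azithromycin dose, as the Risks section has it. Which stopping statement is right is for the investigators.

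The cost is wording, plus recording reaction and last-dose dates at the biweekly contacts already planned. There are two downsides. Post-drug events move to the supporting table. Censoring at the last dose may be informative if families stop without a recorded reaction, and Limitations already anticipates non-adherence. The full-window count therefore stays as a check.

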children with cystic fibrosis or bronchiectasis, because the prophylactic use of macrolides has already demonstrated value and become usual care for these patients. Children with cardiac arrhythmias will be excluded, due to the potential increase in cardiovascular death that has been shown in the adult population. Patients with cyanotic heart disease would be excluded. Children with colitis will also be excluded due to the potential effects to the gastrointestinal flora. In addition, any child with a known macrolide allergy or child who is taking any medication that has a known interaction with macrolides, and any child with kidney or liver failure will also be excluded. Patients with short-bowel syndrome would also be excluded due to malabsorption of medication.

Once patients are screened for eligibility, families will be approached, either over the phone or at a regularly scheduled office visit. Informed written consent will be obtained in the clinic from the parent or legal guardian of each eligible child by any of the co-investigators or the research nurse at the time of enrollment. Either the research nurse or another clinical member of the HRCC team will then collect a nasal aspirate sample at the first study visit (description in Laboratory section). The nasal aspirate will be stored and studied after the conclusion of the treatment phase for its levels of myleoperoxidase, cytokines, respiratory virology, and micro biome. In addition, all patients 2 and older will have a spirometry reading performed using a TremoFlo airway oscillometry system (iOS) manufactured by Thorasys. With the iOS, the child breathes normally into the machine and lung function is measured by a gentle multi-frequency airway against the patient's respiratory airflow. A baseline EKG will be obtained on all patients.

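### Death is in no outcome: a death without a visit falls outside the event part of the safety aim, and the visit totals take no account of follow-up that a death removes

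*Combined protocol and SAP*

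**What the plan says.** The primary aim is to "reduce the total number of unscheduled face-to-face physician visit for respiratory related illness in a clinic, urgent care, emergency room or hospital setting", counted "during the 3-6 month study period, and subsequent 2 months follow-up". Study Outcomes, item 1, describes the encounters as "defined as unscheduled sick visits, emergency room visits, and hospital admissions".

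The first secondary aim asks whether azithromycin has a similar number of side effects, or of "adverse events leading to unscheduled clinic, urgent care, emergency room or hospital visit as compared to placebo". It has two parts: side effects, with no condition attached, and adverse events, which count only if they lead to a visit. Item 5 of Study Outcomes mentions only the first part: "We expect no significant difference in adverse side effects between the treatment group receiving the macrolide and the control group receiving the placebo".

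The remaining aims and outcomes cover cost, respiratory samples, oscillometry and visits in the following 12 months. The closing list under Interpretation and Potential Importance of Findings adds no mortality item. As a possible harm of the drug, death appears once in the protocol's text, in the exclusion criteria. Children with arrhythmias are excluded "due to the potential increase in cardiovascular death that has been shown in the adult population".

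The Data Analysis Plan relates total hospital days, ER visits and unscheduled clinic visits to treatment, by intention to treat, with logistic regression and a random intercept. It states no time at risk, no rule for a child who dies, and no competing or composite event. The sample size section, by contrast, works with a rate per child-year.

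**The concern.** There are two separate gaps.

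The first is in safety. The exclusion criteria acknowledge a fatal harm reported in adults, yet the plan has no outcome in which a death must be counted. A death that produces no visit cannot meet the event part of the safety aim. Whether it counts as a side effect would be decided after it happened. The population makes this more than a formality: the High Risk Children's Clinic selects on recent ED visits, hospitalizations or a PICU stay, and tracheostomy with chronic ventilation is a stratification factor. With about 46 children per arm, every death needs to appear in the comparison under a rule set in advance.

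The second is in efficacy. A child who dies stays in the intention-to-treat set but adds no further encounters. In an analysis of totals without time at risk, that lost time looks the same as time alive and well.

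**Working it through.** **Inputs.** From Overview: 92 children. From Study Procedures: half per arm, hence 46. From the sample size section: 1.6 encounters per child-year in controls, SD 1.66, difference 1, 45 per group, two-sided alpha 0.05. From the primary aim: 3–6 months plus 2, so 5–8 months per child. From Study Outcomes: a 20% reduction expected. The documents give no mortality figure, so the number and timing of deaths below are assumptions.

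**The plan's own figure.** n per group = 2 × (1.96 + 0.84)² × 1.66² / 1² ≈ 43.3, rounded up to 44. A t-test calculation gives 44.2, so 45 per group, with power 80.7% at 45. The stated 90 children and 80% power reproduce. The standard error of the difference is 1.66 × √(2/45) = 0.35 encounters per child-year.

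**Effect of one death on an arm's total.** Assume the child has the arm's average expected encounters and that these are spread evenly over follow-up.
- Expected encounters per child: 1.6 × 5/12 = 0.67 to 1.6 × 8/12 = 1.07.
- Death at the very start: all of these are lost. The share of the arm total is 1/46 = 2.2%. The arm mean falls by 0.67/46 = 0.015 to 1.07/46 = 0.023 encounters.
- Death midway: half of that, 1.1%.
- Five deaths at the start, all in one arm: 5/46 = 10.9%.

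**Against the plan's effects.**
- In the sample size section's unit, a death at the start shifts the mean by 1.6/46 = 0.035 per child-year. That is 3.5% of the difference of 1, and 0.035/0.35 = one tenth of the standard error.
- Against the 20% reduction, it is 2.2/20 = 11%.
- If a child who dies would have had twice the average encounters (assumption), these figures double: 2/46 = 4.3%, or a fifth of the standard error.

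**Balance.** Suppose a deaths in one arm and b in the other, all at the start. The ratio of totals is then multiplied by (46 − a)/(46 − b).
- One against none: 45/46 = 0.978.
- Three against one: 43/45 = 0.956.
- Equal numbers: 1, so no bias.

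**How likely is at least one death?** With an assumed risk r over follow-up, the expected number is 92r and the chance of at least one is 1 − (1 − r)^92.

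| r (assumed) | Expected deaths in 92 | Chance of at least one |
|---|---|---|
| 0.5% | 0.5 | 37% |
| 1% | 0.9 | 60% |
| 2% | 1.8 | 84% |
| 5% | 4.6 | 99% |

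So even at low assumed risks the plan may well have to handle a death, while the resulting shift in the encounter comparison stays small.

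**The case against.** The strongest reply is that a death would not go unnoticed. Study Procedures provides for biweekly contact, the Risks section extends monitoring to any other unexpected outcome, and Overview keeps children who stop the medication under clinical follow-up. This stands: a reader might infer that deaths at home would be missed, and the documents do not support that. What the reply does not supply is a planned between-arm comparison that includes the death.

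A second reply is that the side-effect part of the aim carries no visit condition, so a death could be counted there. That is possible, but it depends on attributing the death to treatment case by case, and the plan does not say that this will be done.

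Third, a reader might infer from the exclusion criteria that the protocol expects sudden deaths on azithromycin in these children. It does not. The sentence concerns cardiovascular death in adults, says nothing of sudden death or death at home, and accompanies the exclusion of children with arrhythmias; a baseline EKG is also required.

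Fourth, a death does not always lower a child's count. Hospital days are among the totals, and a long final admission may add many. The statement holds only relative to what the child would have accrued with full follow-up.

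Finally, missing time at risk is a wider matter. Recruitment runs from October to December with a common end of treatment on 31 March, so follow-up varies for every child. This is true, and it strengthens the case for the second change below.

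**Conclusion.** The point holds as a gap in the definition of outcomes, chiefly on the safety side. No outcome includes death, and the event part of the safety aim cannot count one that led to no visit. That follows from the text and needs no assumption about mortality.

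The efficacy consequence is real in direction but small. A reader might infer that one or two deaths could produce an apparent benefit of azithromycin. The figures do not support that. The 2.2% per death is a ceiling that requires death at the start of follow-up in a child with average expected encounters, and it is about a tenth of the standard error. Only an imbalance between arms biases the comparison; if treatment does not affect mortality or its timing, the expected net bias is zero. Several early deaths in one arm would be needed to approach half of the 20% reduction. How many deaths to expect cannot be determined from the documents.

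**What to change.** 1. Name all-cause death from randomisation to 31 May of the child's season as a secondary safety outcome, reported by arm and counted whether or not a visit occurred and whatever its attributed cause.

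2. Analyse encounters per child-time at risk, for example with a log follow-up-time offset, with time ending at death or at the end of follow-up. This agrees with the per-child-year rate in the sample size section and also handles the planned 5–8 month variation. A log-time offset belongs in a count model with a log link, so the reference to logistic regression would have to be reworded for this outcome.

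I would not add an analysis that gives a child who dies the highest observed count. If that maximum were 5–10 encounters (assumption), one such child would move the arm mean by 5/46 = 0.11 to 10/46 = 0.22. The shift to be addressed is 0.015–0.023, so this overshoots about 5- to 15-fold and depends on a single outlying child.

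The cost is plan wording and one added row in the safety table. Enrolment, visits and care are unchanged. The limitation is that a while-alive rate describes children only while they live, so it must be read alongside the deaths by arm.
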